# **Risks, Burdens and Benefits**

16. In medical practice and in medical research, most interventions involve risks and burdens.

Medical research involving human subjects may only be conducted if the importance of the objective outweighs the risks and burdens to the research subjects.

17. All medical research involving human subjects must be preceded by careful assessment of predictable risks and burdens to the individuals and groups involved in the research in comparison with foreseeable benefits to them and to other individuals or groups affected by the condition under investigation.

Measures to minimise the risks must be implemented. The risks must be continuously monitored, assessed and documented by the researcher.

18. Physicians may not be involved in a research study involving human subjects unless they are confident that the risks have been adequately assessed and can be satisfactorily managed.

When the risks are found to outweigh the potential benefits or when there is conclusive proof of definitive outcomes, physicians must assess whether to continue, modify or immediately stop the study.

# **Vulnerable Groups and Individuals**

19. Some groups and individuals are particularly vulnerable and may have an increased likelihood of being wronged or of incurring additional harm.

All vulnerable groups and individuals should receive specifically considered protection.

20. Medical research with a vulnerable group is only justified if the research is responsive to the health needs or priorities of this group and the research cannot be carried out in a non-vulnerable group. In addition, this group should stand to benefit from the knowledge, practices or interventions that result from the research.

## **Scientific Requirements and Research Protocols**

21. Medical research involving human subjects must conform to generally accepted scientific principles, be based on a thorough knowledge of the scientific literature, other relevant sources of information, and adequate laboratory and, as appropriate, animal experimentation. The welfare of animals used for research must be respected.

22. The design and performance of each research study involving human subjects must be clearly described and justified in a research protocol.

The protocol should contain a statement of the ethical considerations involved and should indicate how the principles in this Declaration have been addressed. The protocol should include information regarding funding, sponsors, institutional affiliations, potential conflicts of interest, incentives for subjects and information regarding provisions for treating and/or compensating subjects who are harmed as a consequence of participation in the research study.

In clinical trials, the protocol must also describe appropriate arrangements for post-trial provisions.

#### **Research Ethics Committees**

23. The research protocol must be submitted for consideration, comment, guidance and approval to the concerned research ethics committee before the study begins. This committee must be transparent in its functioning, must be independent of the researcher, the sponsor and any other undue influence and must be duly qualified. It must take into consideration the laws and regulations of the country or countries in which the research is to be performed as well as applicable international norms and standards but these must not be allowed to reduce or eliminate any of the protections for research subjects set forth in this Declaration.

The committee must have the right to monitor ongoing studies. The researcher must provide monitoring information to the committee, especially information about any serious adverse events. No amendment to the protocol may be made without consideration and approval by the committee. After the end of the study, the researchers must submit a final report to the committee containing a summary of the study's findings and conclusions.

#### Privacy and Confidentiality

24. Every precaution must be taken to protect the privacy of research subjects and the confidentiality of their personal information.

# Informed Consent

25. Participation by individuals capable of giving informed consent as subjects in medical research must be voluntary. Although it may be appropriate to consult family members or community leaders, no individual capable of giving informed consent may be enrolled in a research study unless he or she freely agrees.

26. In medical research involving human subjects capable of giving informed consent, each potential subject must be adequately informed of the aims, methods, sources of funding, any possible conflicts of interest, institutional affiliations of the researcher, the anticipated benefits and potential risks of the study and the discomfort it may entail, post-study provisions and any other relevant aspects of the study. The potential subject must be informed of the right to refuse to participate in the study or to withdraw consent to participate at any time without reprisal. Special attention should be given to the specific information needs of individual potential subjects as well as to the methods used to deliver the information.

After ensuring that the potential subject has understood the information, the physician or another appropriately qualified individual must then seek the potential subject's freely-given informed consent, preferably in writing. If the consent cannot be expressed in writing, the non-written consent must be formally documented and witnessed.

All medical research subjects should be given the option of being informed about the general outcome and results of the study.

27. When seeking informed consent for participation in a research study the physician must be particularly cautious if the potential subject is in a dependent relationship with the physician or may consent under duress. In such situations the informed consent must be sought by an appropriately qualified individual who is completely independent of this relationship.

28. For a potential research subject who is incapable of giving informed consent, the physician must seek informed consent from the legally authorised representative. These individuals must not be included in a research study that has no likelihood of benefit for them unless it is intended to promote the health of the group represented by the potential subject, the research cannot instead be performed with persons capable of providing informed consent, and the research entails only minimal risk and minimal burden.

29. When a potential research subject who is deemed incapable of giving informed consent is able to give assent to decisions about participation in research, the physician must seek that assent in addition to the consent of the legally authorised representative. The potential subject's dissent should be respected.

30. Research involving subjects who are physically or mentally incapable of giving consent, for example, unconscious patients, may be done only if the physical or mental condition that prevents giving informed consent is a necessary characteristic of the research group. In such circumstances the physician must seek informed consent from the legally authorised representative. If no such representative is available and if the research cannot be delayed, the study may proceed without informed consent provided that the specific reasons for involving subjects with a condition that renders them unable to give informed consent have been stated in the research protocol and the study has been approved by a research ethics committee. Consent to remain in the research must be obtained as soon as possible from the subject or a legally authorised representative.

31. The physician must fully inform the patient which aspects of their care are related to the research. The refusal of a patient to participate in a study or the patient's decision to withdraw from the study must never adversely affect the patient-physician relationship.

32. For medical research using identifiable human material or data, such as research on material or data contained in biobanks or similar repositories, physicians must seek informed consent for its collection, storage and/or reuse. There may be exceptional situations where consent would be impossible or impracticable to obtain for such research. In such situations the research may be done only after consideration and approval of a research ethics committee.

# Use of Placebo

33. The benefits, risks, burdens and effectiveness of a new intervention must be tested against those of the best proven intervention(s), except in the following circumstances:

Where no proven intervention exists, the use of placebo, or no intervention, is acceptable; or

Where for compelling and scientifically sound methodological reasons the use of any intervention less effective than the best proven one, the use of placebo, or no intervention is necessary to determine the efficacy or safety of an intervention

and the patients who receive any intervention less effective than the best proven one, placebo, or no intervention will not be subject to additional risks of serious or irreversible harm as a result of not receiving the best proven intervention.

Extreme care must be taken to avoid abuse of this option.

# **Post-Trial Provisions**

34. In advance of a clinical trial, sponsors, researchers and host country governments should make provisions for post-trial access for all participants who still need an intervention identified as beneficial in the trial. This information must also be disclosed to participants during the informed consent process.

#### **Research Registration and Publication and Dissemination of Results**

35. Every research study involving human subjects must be registered in a publicly accessible database before recruitment of the first subject.

36. Researchers, authors, sponsors, editors and publishers all have ethical obligations with regard to the publication and dissemination of the results of research. Researchers have a duty to make publicly available the results of their research on human subjects and are accountable for the completeness and accuracy of their reports. All parties should adhere to accepted guidelines for ethical reporting. Negative and inconclusive as well as positive results must be published or otherwise made publicly available. Sources of funding, institutional affiliations and conflicts of interest must be declared in the publication. Reports of research not in accordance with the principles of this Declaration should not be accepted for publication.

## **Unproven Interventions in Clinical Practice**

37. In the treatment of an individual patient, where proven interventions do not exist or other known interventions have been ineffective, the physician, after seeking expert advice, with informed consent from the patient or a legally authorised representative, may use an unproven intervention if in the physician's judgement it offers hope of saving life, re-establishing health or alleviating suffering. This intervention should subsequently be made the object of research, designed to evaluate its safety and efficacy. In all cases, new information must be recorded and, where appropriate, made publicly available.

Disclaimer: © 2013 World Medical Association, Inc. All Rights Reserved. All intellectual property rights in the Declaration of Helsinki are vested in the World Medical Association. Previous permissions granted to publish or reproduce otherwise WMA policy don't apply to this version of the Declaration of Helsinki until January 1st, 2014. For further questions, please contact the WMA secretariat at [contact].

#### Annex 3: Division of AIDS table for grading the severity of adverse events

http://www.niaid.nih.gov/labsandresources/resources/daidsclinrsrch/documents/daids aegradingtable.pdf

Statistical Analysis Plan

Isala study: Analytical treatment interruption in HIV positive patients with low viral reservoir to evaluate the potential of a functional cure

Date:	4 July 2018			
Author:	[name] Biostatistician, Institute of Tropical Medicine, Antwerp, Belgium			
Approved by:	Coordinating Investigator [name]			
	Date: / / //			

Table of Contents

1. Int	roduction	.2
2. St	udy design and objectives	.2
2.1.	Study design	.2
2.2.	Study objectives and Hypotheses	.2
2.3.	Variables of interest	.3
3. De	escription of study population	.3
3.1.	Analysis populations	.3
3.2.	Patient accounting	.3
3.3.	Description of study population	.4
4. Sta	atistical Methods	.4
4.1.	Primary Objective	.4
4.2.	Secondary Objectives	.4
4.3.	Exploratory Objective	.5
4.4.	Subgroup Analysis	.5
5. Ex	ample Tables and Figures	.5

1. Introduction

This Statistical Analysis Plan (SAP) provides a description of the main, pre-planned analyses for the Isala study. The purpose of this study is to demonstrate that treatment interruption of longstanding combined antiretroviral therapy (cART) in participants with very low proviral reservoir results in "functional cure". The study conduct is described in Protocol ITM0714.

These planned analyses will be performed by the statistician at the Clinical Trials Unit of the Institute of Tropical Medicine (Antwerp) in collaboration with the coordinating investigator. The analysis results will be described in a statistical analysis report, to be used as the basis of the primary research. This document describes statistical methods for the primary, secondary and tertiary outcomes of the study as defined by protocol. Additional analyses may be performed but are not covered by the current analysis plan. Statistical methods for these additional analyses will be described together with the results.

This analysis plan will be finalized and approved before final database lock. Major changes in statistical methodology used for the main and pre-planned analyses from this SAP, which is finalized before database lock, will require detailed description and justification in the statistical analysis report. The final analysis datasets, programs, and outputs are archived following good clinical practice guidelines (ICH E9).

2. Study design and objectives

2.1. Study design

This is a single arm multi-centric non-randomized (prospective) clinical trial. The study will be divided in two parts. The first one will aim at quantifying the HIV reservoir in a large group of patients under ART with strictly predefined inclusion and exclusion criteria. The second step encompasses an analytical treatment interruption among participants with the lowest viral reservoir.

2.2. Study objectives and Hypotheses

Primary Objective

The primary objective is to determine the proportion of post treatment controllers (PTC) (i.e. patients under cART with low baseline peripheral blood proviral DNA that will show sustained viral suppression at 48 weeks post treatment interruption (TI).

Secondary Objectives

a. To confirm the safety of a TI strategy in selected HIV patients

b. To assess the viral reservoir magnitude prior, during and after TI

c. To assess the viral and host dynamics in those participants with viral rebound post TI.

Exploratory Objective

- a. The identification of predictors (clinical and/or laboratory) of PTC phenotype.
- b. The identification of predictors for viral rebound over time.

2.3. Variables of interest

Primary: The proportion of participants with plasma viral load (pVL) below the lower limit of detection (< 50 HIV RNA copies/ml plasma) 48 weeks following interruption of ART.

Secondary:

- The numbers and percentages of AE's and SAE's during the whole study period.
- Viral reservoir (total HIV-1 DNA) and viral transcription (total HIV-1 cellassociated RNA) measurements at every visit between baseline (just before TI) until viral rebound and 12 weeks after viral rebound.
- Repeated pVL measurements.

Exploratory: Potential clinical and/or laboratory variables, such as demographic and epidemiological data, medical history (past and current), vital parameters, ultrasensitive HIV viral load, CD4 T cell count and laboratory test data (e.g. hemoglobin, ANC, platelets, creatinine, AST & ALT), viral reservoir (quantitative viral outgrowth measurement) and viral release measurements (spontaneous and stimulated) at baseline.

3. Description of study population

3.1. Analysis populations

The statistical analyses will be performed on all participants enrolled in the study and who met all inclusion and exclusion criteria. Complete case analysis will be performed for all statistical analyses.

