• Adequate peripheral vein access to perform leukapheresis

Participants meeting any of the following exclusion criteria will not be enrolled in the study:

- Previous or current history of AIDS defining event as defined in category C of the CDC clinical classification[39] .
- Any acute infection or serious medical illness within 60 days prior to study entry. Participants will be excluded from this study for a serious illness (requiring systemic treatment and/or admission) until the subject either completes therapy or is clinically stable on therapy, in the opinion of the Investigator, for at least 14 days prior to study entry
- History of resistance to antiretroviral drugs, documented by genotyping.
- Active hepatitis B or C virus infection: as defined with a positive serology for either disease with signs of active viral replication?
- Significant risk of HIV transmission during treatment interruption in the opinion of the investigator. This includes evidence for unsafe sexual contacts.
- Current or past history of cardiomyopathy or significant ischemic or cerebrovascular disease.
- History of HIV-related thrombocytopenia.
- Active renal disease (defined as a glomerular filtration rate (calculated by MDRD equation) below 50 ml/min or the presence of HIV associated nephropathy in the past medical history.

- Current or known history of cancer (with the exception of in situ cervix carcinoma or squamous cell carcinoma of the skin) within five years prior to screening.
- Pregnancy and breastfeeding.
- Any condition, including psychiatric and psychological disorders that might interfere with adherence to study requirements or safety of the participant.
- Prior use of any HIV vaccine and/or non-established experimental therapy
- Any of the following laboratory test results at screening:
  - 1. Confirmed hemoglobin <11g/dl for women and <12 g//dl for men
  - 2. Confirmed platelet count  $< 90,000/\mu$ l
  - 3. Confirmed neutrophil count <1200/µl
  - 4. Confirmed AST and/or ALT > 5 x upper limit on normal range (ULN). One retest within 14 days is allowed.
- Receipt of any immune modulator or suppressor within 30 days prior study entry, including, but not limited to drugs such as corticosteroids (with the exception of corticosteroids used for topical use), granulocyte-macrophage colony-stimulating factor, interleukin (IL)-2, IL-7 and IL-15.

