# **5.1.1 FIRST ELIGIBILITY SCREENING AND INCLUSION IN THE FIRST PART OF THE STUDY** (RESERVOIR MEASUREMENT STUDY)

Study participants will be selected from the four participating clinical centers. Screening evaluations to determine eligibility must be completed within 7 days prior to study entry.

The patient will be invited to participate in the trial and provided information about the aims and risks of the project. After obtaining written informed consent (first written informed consent), clinical eligibility will be assessed. Patients will be eligible for enrollment if they fulfill all of the inclusion criteria described in section 4.2. Patients will not be eligible for the study if they meet any of the above described exclusion criteria.

3x9ml blood will be drawn in order to evaluate the magnitude of the viral reservoir. This sample will be sent to UZ Gent for quantification of total HIV DNA and unspliced cell-associated RNA. More information on the method used is to be found in section 5.3 of the protocol.

The following will be assessed at this visit:

- Assessment of subject eligibility according to the inclusion and exclusion criteria
- Demographic and epidemiological data
- Medical history (past and current), including HIV-associated conditions
- Full antiretroviral history (including result of resistance assays if available)
- Review of non-antiretroviral medication within the last 30 days
- Physical examination including vital parameters, height and weight
- HIV viral load and CD4 T cell count.

- Laboratory test (non-fasting): hemoglobin, absolute neutrophil count (ANC), platelets, creatinine, liver enzymes AST & ALT. Hepatitis HCV & HBV serology if necessary.

- Pregnancy test among women.

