# 8.3 Statistical methods

### 8.3.1 Population to be analyzed

The statistical analyses will be performed on all enrolled participants.

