3.2. Patient accounting

The numbers of participants screened, enrolled and excluded will be presented. Excluded participants will be summarized by reason for exclusion in a CONSORT flow diagram by the PI.

All patients who conform to all inclusion and exclusion criteria and are enrolled into the study will be tabulated. The number of patients discontinued will be tabulated by reason for study discontinuation (Completed the study, Lost to Follow Up, Withdrawal of Consent, Discontinuation of drug for Safety or Other Reasons, Death, Other) (Example Table 1). This information will also be described separately in a CONSORT flow diagram.

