4.1. Primary Objective

The primary objective will be assessed by estimating the proportion of participants with undetectable viral load (<50 HIV RNA copies/ml plasma) 48 weeks after interruption of ART. A 95% CI for the proportion will be calculated using Wilson's score method (Example Table 3). Respective proportions at different time points (week 2, 4, 6 and 8) will be also calculated for descriptive purposes.

4.2. Secondary Objectives

Adverse events (AEs) will be coded using the Medical Dictionary for Regulatory Activities (MEDDRA) and will be reported based on MEDDRA preferred terms and body systems. All AEs will be analyzed based on counts of patients with a specific category and not on counts of individual adverse events. The relationship between AEs and ARV interruption is determined by the investigator and categorized as "drugrelated" if unlikely, possibly, likely or definitely related to treatment interruption. All AEs definitely unrelated to intervention will also be used to examine the relationship between AEs and intervention.

All AEs and all serious AEs from the beginning of treatment interruption until the end of the study (end of follow-up period) are reported. AE counts will be summarized for the whole study period (treatment interruption and follow-up period). Counts (%) of patients with AEs, drug-related AEs and serious AEs will be presented by Meddra body system and preferred term together with a 95% Wilson confidence interval (Example Table 4 and 5).

Reservoir replenishment and HIV viral load kinetics following ART interruption will be summarized in terms of medians and interquartile ranges (Example Table 3). No formal statistical testing will be done in these results. If present, pVL rebound will be represented graphically with a spaghetti plot. Furthermore, the measurements over time of viral load rebound and viral reservoir will be presented graphically for every patient included in the study (one line for every patient over time).

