4.3. Exploratory Objective

Potential predictors of post-treatment control (end of second part of the study) will be assessed by Fisher's exact test at 5% significance level (Example Table 6). The time to viral rebound will be assessed by survival analysis methodology, e.g. Kaplan-Meier estimates and curves (Example table 7). Potential predictors of viral rebound will be examined by single Cox regression models (Example Table 8).

4.4. Subgroup Analysis

No subgroup analyses will be performed in this study due to the small sample size .

5. Example Tables and Figures

Example Table 1: Patient Accounting

	n (%)
Screened	ХХ
Excluded	xx (xx %)
[add reason for exclusion]	xx (xx %)
	xx (xx %)
Enrolled to the first stage	xx (xx %)
- Completed the study	xx (xx %)
- Early withdrawals	xx (xx %)
- Lost to follow-up	xx (xx %)
- Consent withdrawal	xx (xx %)
Excluded from second stage	
Enrolled to the second stage	xx (xx %)
- Completed the study	xx (xx %)
- Early withdrawals	xx (xx %)
- Lost to follow-up	xx (xx %)
- Consent withdrawal	xx (xx %)

Example Table 2: Baseline Characteristics at Recruitment

	n (%)
Ν	XX
Epidemiological findings	
Age (yr): median (IQR)	xx (xx - xx)
Gender: male (%)	xx (xx)
female (%)	xx (xx)
Ethnicity: [add ethnic categories]	
Transmission route: [add categories]	
Duration of HIV infection (months/years): median (IQR)	
Total duration of antiviral treatment (months): median (IQR)	
Clinical findings	
Last antiviral treatment: PI+ NRTI	xx (xx)
NNRTI+NRTI	xx (xx)
II+ NRTI	xx (xx)
other	xx (xx)

xx (xx - xx)
xx (xx - xx)

Example Table 3: Summary of Primary and Secondary Analysis Results

	n/N (%, 95% Cl)
Primary analysis	
Number of participants with undetectable viral load (<50 HIV	xx/xxx
RNA copies/ml plasma) 48 weeks after interruption of ART	(xx; xx - xx)
Number of participants with undetectable viral load (<50 HIV RNA copies/ml plasma) at week:	
- 2	xx/xxx
	(xx; xx - xx)
- 4	xx/xxx
	(xx; xx - xx)
- 6	xx/xxx
	(xx; xx - xx)
- 8	xx/xxx
	(xx; xx - xx)
Secondary analysis	
Viral Reservoir at baseline (/10*6 PBMC's): median (IQR)	xx (xx - xx)
Viral Reservoir after TI (/10*6 PBMC's): median (IQR)	xx (xx - xx)
Viral load rebound by week (in copies/ml plasma): median (IQR)	
- 0 (baseline)	xx (xx - xx)
- 2	xx (xx - xx)
- 4	xx (xx - xx)
- 8	xx (xx - xx)

Example Table 4: Counts of patients (%) with Adverse Events by Body System and Preferred Term (Meddra)

	(N=xx) n(%)
Blood and Lymphatic System	xx (xx)
Anaemia	xx (xx)

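### SAP 3.1 limits every analysis to enrolled participants who met the eligibility criteria, whereas protocol 8.3.1 analyses all enrolled; for the treatment-interruption part the condition should be removed (minor)

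*SAP*

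**What the plan says.** Protocol 8.3.1 sets the population in one sentence: "The statistical analyses will be performed on all enrolled participants". SAP 3.1 is the only population rule in the SAP. It states that the analyses will be "performed on all participants enrolled in the study and who met all inclusion and exclusion criteria" and continues: "Complete case analysis will be performed for all statistical analyses". Neither document names a separate safety set.

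SAP 3.2 pairs the same two conditions for patient accounting: "All patients who conform to all inclusion and exclusion criteria and are enrolled into the study will be tabulated". SAP 4.2 reports "All AEs and all serious AEs from the beginning of treatment interruption until the end of the study" and presents patient counts and percentages with Wilson intervals. Example Tables 4 and 5 give the denominator only as a placeholder.

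The protocol makes eligibility a gate to enrolment. Section 4.2 says "Participants meeting any of the following exclusion criteria will not be enrolled in the study", section 5.1.1 says "Patients will not be eligible for the study if they meet any of the above described exclusion criteria", and section 5.1.5 has the criteria checked again at the baseline visit, before ART is stopped.

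**The concern.** The intervention is stopping ART, and protocol 7.1 ties an adverse event to a subject with treatment interruption, whatever that subject's eligibility. Safety percentages should therefore count everyone who stopped. The SAP's added condition would remove an exposed participant from both the primary and the safety denominators if ineligibility came to light after interruption. That could happen. Several criteria rest on history (nadir CD4, past resistance, past AIDS events), and these can be corrected at a later source check. Protocol 5.1.5 also takes blood tests at the baseline visit without saying whether the results are awaited before interruption. In a single-arm open study, the eligibility judgement could then be made with the outcome already known.

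With 2 to 5 controllers expected (protocol 4.3, step 5), one person is a visible share of the numerator.

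**Working it through.** **Inputs.** Planned number stopping ART: 32 (protocol 8.4). Expected controllers: 2 to 5 (protocol 4.3). Interval: 95% Wilson (protocol 8.3.3, SAP 4.1). The number of participants enrolled in error is not given, so one person is assumed for illustration.

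**The plan's own figure.** Wilson interval: centre = (p + z²/2n)/(1 + z²/n); half-width = z·√[p(1−p)/n + z²/4n²]/(1 + z²/n); z = 1.96.
- 2/32: centre 10.9%, half-width 9.2, interval 1.7% to 20.1%, width 18.4 points.
- 5/32: centre 19.3%, half-width 12.4, interval 6.9% to 31.8%, width 24.9 points.

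These match the 18 to 25 points in protocol 8.4. Exact rates of 5% and 15% give 17.2 and 24.6, so the stated range corresponds to whole-patient counts.

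**Removing one of N participants, x of them controllers.**
- Non-controller removed: x/(N−1) − x/N = x/[N(N−1)].
- Controller removed: (x−1)/(N−1) − x/N = −(N−x)/[N(N−1)].

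At N = 32, N(N−1) = 992:

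| Person removed | All 32 kept | One removed | Shift (points) |
|---|---|---|---|
| Non-controller | 2/32 = 6.3% (1.7–20.1) | 2/31 = 6.5% (1.8–20.7) | 2/992 = +0.2 |
| Non-controller | 5/32 = 15.6% (6.9–31.8) | 5/31 = 16.1% (7.1–32.6) | 5/992 = +0.5 |
| Controller | 2/32 = 6.3% (1.7–20.1) | 1/31 = 3.2% (0.6–16.2) | −30/992 = −3.0 |
| Controller | 5/32 = 15.6% (6.9–31.8) | 4/31 = 12.9% (5.1–28.9) | −27/992 = −2.7 |

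**Effect of the complete-case rule.** Missing week-48 results would lower the denominator. For assumed denominators from 24 to 32, the shift runs from +0.2 to +0.9 points (non-controller; at 24, 5/552 = 0.9) and from −2.7 to −4.0 points (controller; at 24, −22/552 = −4.0). If the person has no week-48 result, the complete-case rule already removes them and the clause changes nothing in the primary analysis.

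**Safety, extreme case.** If the removed person had the only SAE, 1/32 = 3.1% (0.6–15.7) becomes 0/31 = 0% (0–11.0).

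**Is there another denominator for safety?** The SAP 4.2 sentence fixes which events are reported and over what period. It does not say who is in the denominator. SAP 3.1 is therefore the only rule that a programmer could apply to the percentages.

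**The case against.** The strongest reply is that the clause is shorthand for eligible and enrolled. Anyone meeting an exclusion criterion is not to be enrolled, the criteria are checked again before ART is stopped, and SAP 3.2 uses the same pairing. On that reading the two populations are identical. This is plausible and is why the effect may be zero. It does not cover ineligibility found after interruption, and it leaves the two documents worded differently.

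A second reply is that the clause may serve part one. Consent comes before the eligibility assessment (protocol 5.1.1), the first inclusion step is itself used to verify the criteria (5.2), and the database holds everyone screened (10.3). The clause may simply keep consented screen failures out of the part-one summaries. This stands: a reader might infer that the clause should be deleted throughout, but that would leave part one undefined.

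A reader might also infer that a removal would be hidden, because Example Table 1 has no line for ineligibility beneath "Enrolled to the second stage". The documents do not support that. SAP 3.2 requires exclusions to be summarised by reason in a CONSORT diagram and discontinuations to be tabulated by reason with an open category, and the tables are only examples. The removal could be shown, although the template has no row for it.

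The word all in SAP 4.2 does favour including every interrupted participant in the AE reporting, but it leaves the percentage denominator ambiguous.

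Finally, if ineligibility is unrelated to viral control, the expected shift in the proportion is zero. That is correct on average, but the single realised result can still move either way.

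**Conclusion.** The discrepancy between SAP 3.1 and protocol 8.3.1 is real and unexplained. Applied as written, the SAP rule would drop an exposed but ineligible participant from the primary and safety percentages. The severity is minor. The documents point to no such case. For one person of 32 the primary moves by +0.2 to +0.5 points (non-controller, the likelier outcome at a 5 to 15% control rate) or −2.7 to −3.0 points (controller). Both are small against a planned width of 18 to 25 points, and the primary result is an estimate with no decision threshold.

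A reader might infer that safety oversight is weakened. It is not: all SAEs are line-listed monthly (protocol 7.1) and reviewed individually by the independent safety monitor (7.3). Only the statistical summaries are in question.

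The figures assume one affected person with a week-48 result and the planned 32 participants.

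**What to change.** In SAP 3.1:
- For the treatment-interruption part, remove the eligibility condition. State that the primary and safety analyses include every enrolled participant who interrupted ART, whatever is later found about eligibility. This clarifies the protocol 8.3.1 set for part two and is not identical to its wording, so account separately for anyone enrolled in part two who did not interrupt (leukapheresis falls between enrolment and baseline).
- For part one, state whether consented participants who fail screening are excluded.
- List eligibility deviations.
- Report an eligible-only result for the primary endpoint as a sensitivity analysis only if such a case occurs. It answers a fair question about the selected population that the safety objective names.

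The cost is SAP wording before database lock. No new data or design change is needed. If the clause only restated enrolment, no part-two result changes.
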